6.3 Lifestyle Restrictions

- Starting 72 hours prior to the first dose until the EOS-A visit (or EOS-B visit, if applicable), participants should not engage in intensive exercise except during protocol-specified exercise tests.
- Starting at Screening for both Part A and Part B, participants will be required to abstain from blood or plasma donation until 3 months after the final study visit.

- 
- Daily dosing of MYK-224 should occur at approximately the same time every day.

6.4 Screen Failures (Part A and Part B)

Screen failures are defined as participants who consent to participate in the clinical study but who are not subsequently entered in the study/included in the analysis population.

A minimal set of screen failure information is required to ensure transparent reporting of screen failure participants, to meet the Consolidated Standards of Reporting Trials (CONSORT) publishing requirements, as applicable, and to respond to queries from regulatory authorities. Minimal information includes date of consent, demography, screen failure details, eligibility criteria, and any serious AEs.

6.4.1 *Retesting During Screening or Lead-in Period (for all participants in Part A and as needed in Part B)*

Participant Re-enrollment: This study permits the re-enrollment of a participant who has discontinued the study as a pretreatment failure (eg, participant has not been randomized/has not been treated). If re-enrolled, the participant must be re-consented.

Participants who screen fail may be considered for rescreening based on the investigator's discretion, taking into consideration the reason(s) for screen fail. One attempt at rescreening will be allowed, and all procedures must be repeated. Further repeat assessments after rescreening may be conducted only after discussion with the Medical Monitor.

Retesting of laboratory parameters and/or other assessments within any single Screening or Lead-in period will be permitted (in addition to any parameters that require a confirmatory value). Additionally, repeat assessments are allowed if core labs require a repeat submission due to quality and to better assess inclusion/exclusion values.

The most current result prior to the first day of treatment in either Part A or Part B is the value by which study inclusion will be assessed, because it represents the participant's most current clinical state.

Laboratory parameters and/or assessments at Screening may be repeated one time in an effort to find all possible well-qualified participants. Consultation with the Medical Monitor may be needed to identify whether repeat testing of any particular parameter is clinically relevant.

7 STUDY INTERVENTION(S) AND CONCOMITANT THERAPY

Study intervention is defined as any investigational intervention(s), marketed product(s), placebo, procedure(s) or medical device intended to be administered to a study participant according to the study protocol.

Study intervention includes both Investigational [Medicinal] Product (IP/IMP) and Non-investigational/Auxiliary [Medicinal] Product (Non-IP/Non-IMP/AxMP) as indicated in Table 7.1-1.

An IP, also known as IMP in some regions, is defined as a pharmaceutical form of an active substance or placebo being tested or used as a reference in a clinical study, including products already with a marketing authorization but used or assembled (formulated or packaged) differently from the authorized form, or used for an unauthorized indication, or when used to gain further information about the authorized form.

Other medications used as support or escape medication for preventative, diagnostic, or therapeutic reasons, as components of the standard of care for a given diagnosis, may be considered as Non-IMPs/AxMPs.

7.1 Study Interventions Administered

The initial dose and timing of dose titration for each participant is described in [Section 5.1](#).

MYK-224 will be taken in a single oral daily dose, either administered at the investigation site or at home by the participant. Participants will take study drug as directed by the investigator/designee. Participants should be instructed to take the study drug at approximately the same time every day with approximately 8 ounces (240 mL) of water. If a participant forgets to take their daily dose at the usual time, they should take it as soon as they remember. Participants should never take more than 1 dose of study drug within an 8-hour period.

On study visit days, participants should fast for at least 4 hours prior to arrival at the clinical site and study drug dosing should be delayed until after study assessments are complete.

Table 7.1-1: Study Interventions

Cohort Name	Cohort 1 and Cohort 2
Intervention Name	MYK-224
Type	Drug
Dose Formulation	Tablet
Unit Dose Strength(s)	██████ mg
Dosage Level(s)	Once daily oral dose between 2.5 and 50 mg
Route of Administration	Oral
Use	Experimental
IMP and Non-IMP/AxMP	IMP
Sourcing	Provided centrally by the Sponsor
Packaging and Labeling	Study intervention will be provided in bottles. Each bottle will be labeled as required per country requirement.
Current/Former Name(s) or Alias(es)	MYK-224 BMS-986435

Abbreviations: AxMP, Auxiliary Medicinal Products; IMP, Investigational Medicinal Product.

7.2 Method of Study Intervention Assignment

Enrolled participants, including those not dosed, will be assigned sequential screening numbers starting with [REDACTED], (eg, [REDACTED]). Those enrolled participants meeting all inclusion and no exclusion criteria will be eligible to be dosed.

In the case of participant rescreening (see [Section 6.4.1](#)), the participant will be screened utilizing the screening transaction and will be assigned the next sequential number not associated to the previous screening number (eg, participant was screened under [REDACTED], another participant screening number assigned was [REDACTED], patient [REDACTED] is screened again under screening number [REDACTED]). All participant numbers from Part A will be maintained in Part B, even if a screening visit for Part B is performed.

Participant replacement is allowed under certain conditions as outlined in [Section 8.2](#). Replacement participants will be screened and assigned the next sequential screening number.

7.3 Blinding

Not applicable as this is an open-label study; all participants will receive active study intervention; however, all dose adjustments will occur through interactive response technology (IRT) based on TTE data. The bioanalytical laboratory will receive treatment assignments in order to minimize unnecessary analysis of samples.

7.4 Dosage Modification

7.4.1 Part A Dosage Modification

The following dose modification instructions apply to all participants in Part A.

7.4.1.1 Dose Titration (Part A only)

All participants will receive a starting dose of 5-mg oral MYK-224. Dose titration will be based on the central read of each participant's TTE parameters collected 3 weeks (at least 21 days) after dose initiation during each dose titration cycle. [REDACTED]

[figure not shown]
[REDACTED], as outlined in [REDACTED]

Participants in Cohort 2 will follow the same titration scheme unless data from Cohort 1 or the ongoing CV029005 DDI study support an adjusted schedule.

In each participant, [REDACTED]

Once the target dose is reached, participants will proceed to the stable dosing period.

Left ventricular ejection fraction parameters for dose reductions as well as temporary and permanent dose discontinuation are also outlined in [REDACTED]. Both central and local TTE reads taken at any time may be used to guide these decisions as described in [Section 8.1.1.1](#) and [Section 8.1.2.1](#). In addition, a dose reduction to the last tolerated dose or dose interruption or discontinuation for safety may occur at any time during the dose titration period based on the clinical judgment of the investigator in consultation with the Medical Monitor. Following a dose reduction, participants will proceed to the stable dosing period and continue on the new dose for a minimum of 6 weeks.

█ [REDACTED]
█ [REDACTED]
█ [REDACTED]

7.4.1.2 Stable Dosing (Part A only)

[figure not shown]
Participants should continue at stable dosing until the following criteria are met: 1) they have been at their target dose for at least 6 weeks (at least 42 days) AND 2) have received MYK-224 (at any dose or combination of doses) for a total of at least 12 weeks (at least 84 days).

During stable dosing, dose modification may still occur in the form of dose reduction to the last tolerated dose, dose interruption, or discontinuation as needed [REDACTED] This dose change would not affect the total time participants would need to stay on MYK-224 prior to EOT.

An example of a dosing schematic is shown below in [Figure 7.4.1.2-1](#). Only planned down titrations are illustrated. Unplanned down titrations may occur at all dose levels as outlined above.

Figure 7.4.1.2-1: Dosing Schematic (Part A)

Abbreviations: EOS, end of study; EOT, end of treatment; Wk, week.

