12-lead ECG	X	X	X	X	X	12-lead ECGs will be performed in a supine position after 10 minutes of rest at all onsite study visits. 12-lead ECGs should be obtained prior to dosing and before blood sampling at visits where those procedures are also performed. A [REDACTED] post-dose 12-lead ECG will also be performed at the [REDACTED] visit. See Section 9.4.4 .
Cardiac Monitoring Device					X	If participant is wearing a device, it should be removed at [REDACTED], as applicable. See Section 9.4.3 .
ICD Download	X		X	X	X	For participants who have ICDs, information including rhythm strips and events will be downloaded from the ICDs at Screening, [REDACTED], and any unscheduled visits, or as clinically indicated after any ICD discharge interrogation occurring during the study.
Laboratory Tests: Participants should fast for 4 hours prior to arriving at clinic.						
Hematology	X	X	X	X	X	

Table 2-4: EOT/Washout Period/EOS/Unscheduled Visit/ET (Part A - All Participants)

Procedure ^a						Notes
Chemistry	X	X	X	X	X	
Urinalysis	X		X	X	X	
Pregnancy Test (WOCBP)	X		X		X	Urine test at [REDACTED]. Serum test at [REDACTED]
Adverse Event Reporting						
Monitor for Adverse Events (AEs and SAEs)	X	X	X	X	X	All AEs and SAEs will be collected from the date of participant's written consent until 30 days after the final dose of MYK-224 or the final study visit, whichever is longer. SAEs should be approved in the BMS EDC tool within 5 business days of entry.
Pharmacokinetic (PK) Assessments						
PK Assessments	[REDACTED]	[REDACTED]	[REDACTED]	[REDACTED]	[REDACTED]	See Table 9.5-1 for PK sampling schedule. [REDACTED] sample to be collected at [REDACTED].
Efficacy Assessments						
Resting and Valsalva TTE	X	X	X	X	X	Resting and Valsalva TTE should be performed prior to post-exercise echocardiography. See Section 9.1.1.1 and Section 9.1.1.2 .

Table 2-4: EOT/Washout Period/EOS/Unscheduled Visit/ET (Part A - All Participants)

Procedure ^a						Notes
Post Exercise/Stress TTE	X		X	X	X	Following a recommended 4–hour fast. See Section 9.1.1.3 . Post-Exercise/Stress TTE is optional for unscheduled visits.
Clinical Outcome Assessments						
KCCQ-23						
NYHA Functional Classification						
Study Treatment						
MYK-224	X					Final dose will be given at the EOT-A visit to allow for a final set of PK samples. No MYK-224 will be provided during the washout period.
Drug Compliance	X			X	X	Return dosing containers for tablet counts.

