5.1.1.2 Treatment Period (Part A)

The treatment period is designed to identify the target individual dose for each participant. Dose titration will be based on measures taken at steady state (at least 21 days after dose initiation) and occur approximately every 4 weeks. Once the target individual dose has been identified for each participant, the participant will continue to the Stable Dosing period. The Dose Titration period and Stable Dosing period are described below.

Dose Titration Period

The study will include an intra-patient dose titration scheme designed to achieve safe and effective dosing for each participant by determining a target individual dose guided by their own response parameters. Participants who meet all eligibility criteria at Screening will begin study treatment with MYK-224. Dosing will consist of a once daily (QD) oral dose in the form of tablets. All participants will begin at an initial dose of 5 mg of MYK-224, followed by up- or down-titration to doses between 2.5 mg and 50 mg.

Participants will return to the investigational site for [REDACTED] clinic visits as outlined in [Table 2-2](#) and [Figure 5.1.1-1](#). These visits will include PK sample collection, [REDACTED], [REDACTED], safety laboratory collection, 12-lead ECGs, clinical evaluations (eg, vital signs, clinical outcome assessments [COAs], concomitant medication use), and echocardiography.

Dose titration will be based on TTE measures taken at 3 weeks (at least 21 days) post-initiation of each new dose. Participants will repeat this 4-week period as needed to identify their individual target dose. Details on dose titration can be found in [Section 7.4.1.1](#).

Stable Dosing Period

Once the individual target dose is identified, participants will continue dosing until 2 criteria are met: 1) 6 weeks (at least 42 days) total dosing at their target dose (including the 4-week titration period, if applicable); and 2) an overall minimum total treatment period of 12 weeks (at least 84 days) at any dose or combination of doses. See [Section 7.4.1.2](#) for details regarding dose modification during stable dosing and the impact of any modification on the criteria for study completion. During this period, participants will have [REDACTED] clinic visits to collect PK samples, [REDACTED], 12-lead ECG and TTE measures, and safety assessments (see [Table 2-3](#)). The final dose of MYK-224 will be administered in clinic at an end-of-treatment visit.

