5.4 Scientific Rationale for Study Design

This study will be conducted in adult participants with symptomatic oHCM. The study will be open-label, and all participants will receive MYK-224. The purpose of this study is to characterize the safety, tolerability, efficacy, and exposure-response relationship of MYK-224 in participants with oHCM. The optional OLE will additionally [REDACTED] of MYK-224.

Because individual patients may require higher or lower exposures to MYK-224 to achieve clinically relevant improvement in LVOT obstruction, Part A of this study will follow an individualized dose-titration strategy that is guided by clinical response. The study will use intra-participant dose titration to identify the individual target dose and assess the pharmacological effects of that dose at steady state. The initial dose selection and titration levels are based on pre-clinical data as well as data from the FIH trial in healthy volunteers (MYK-224-001). [REDACTED]

See [REDACTED] Section 5.5 for details on dose justification in this study.

Dose titration in this study (Part A) will be based on [REDACTED]. Specifically, [REDACTED] (Section 2). The core laboratory TTE data collected 3 weeks (at least 21 days) following the initiation of each dose will be used to determine dose titration, which if indicated, will occur the following week (4 weeks post-initiation).

In each participant, dose escalation will proceed [REDACTED] until both [REDACTED]. Dose reductions may occur [REDACTED]. The individual target dose for this study is defined as the highest dose where these conditions are met (see [Section 7.4](#)).

Participants will enter the stable dosing period and continue to dose at their individual target dose for a minimum of 6 weeks (at least 42 days) of treatment with their target dose (or the maximum allowable dose), for a total treatment period of at least 12 weeks (at least 84 days). Transthoracic echocardiogram, PK samples, and safety labs will be collected [REDACTED] during the stable dosing period. This will provide sufficient time to evaluate the safety and efficacy of MYK-224 [REDACTED] for the highest tolerated dose in each participant. [REDACTED].

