8.1.3 Post-study Intervention Study Follow-up

Participants who discontinue study intervention may continue to be followed.

- If a participant permanently discontinues treatment, the participant will be asked to undergo an EOT visit as soon as possible after stopping study drug, as outlined in [Table 2-4](#) for Part A and [Table 2-6](#) for Part B, and will remain on study to be evaluated for concomitant medications and clinical assessments through a [REDACTED] washout period and subsequent EOS assessment as outlined in [Table 2-4](#) for Part A and [Table 2-6](#) for Part B.
- If the participant is unwilling or unable to be followed for the duration of the study, they will undergo an ET visit as outlined in [Table 2-4](#) for Part A and [Table 2-6](#) for Part B.

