9.1.1.3 Post-exercise/Stress Echocardiography

Participants will undergo standard post-exercise stress TTEs as outlined/described in [Table 2-1](#) and [Table 2-4](#). Participants should abstain from food for at least 4 hours prior to post-exercise stress TTEs. At all timepoints where both resting and post-exercise measures are taken, resting TTE should be performed prior to post-exercise echocardiography.

Post-exercise echocardiography needs to be acquired within 72 hours of Resting TTE. Instantaneous peak LVOT gradient will be assessed immediately post exercise by TTE. Care should be taken to select the best window and angle when obtaining Doppler signal to assess the LVOT gradient, obtain valid LVOT gradient value, and avoid contamination by MR jet if present (see Echo Instruction Manual). Participants on standard cardiomyopathy therapy (eg, beta-blockers or calcium channel-blockers) should be on the same dose whenever possible and this medication should be administered prior to exercise testing.

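### The EOT-A reading behind the LVOT-effect endpoints can fall before steady state or off drug, and Section 10 has no rule for it

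*Combined protocol and SAP*

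**What the plan says.** Section 10.4.3 reads four LVOT-effect measures at EOT-A: change from baseline in post-exercise, resting and Valsalva peak gradient, and the proportion with resting below 30 and Valsalva below 50 mm Hg.

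The intended condition of that reading is stated. Section 5.4 says the study will identify the individual target dose and "assess the pharmacological effects of that dose at steady state". Section 5.1.1.2 bases titration on "measures taken at steady state (at least 21 days after dose initiation").

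Other rules decide when EOT-A actually falls:

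- **Reduction during titration (Section 7.4.1.1):** "Following a dose reduction, participants will proceed to the stable dosing period and continue on the new dose for a minimum of 6 weeks".
- **Dose change during stable dosing (Section 7.4.1.2):** reduction, interruption and discontinuation are allowed, and "This dose change would not affect the total time participants would need to stay on MYK-224 prior to EOT".
- **Permanent discontinuation (Section 8.1.3):** "the participant will be asked to undergo an EOT visit as soon as possible after stopping study drug".
- **EOT-A in Table 2-4:** "Final dose will be given at the EOT-A visit to allow for a final set of PK samples", and no drug is supplied in washout.
- **Post-exercise echo (Section 9.1.1.3):** "Post-exercise echocardiography needs to be acquired within 72 hours of Resting TTE".

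The Efficacy/PD set (Section 10.3) keeps anyone dosed who has a baseline and one post-baseline value. Section 10.4 gives no rule for EOT-A readings after a dose change, after discontinuation, or when the echo is missing. The responder definition has no on-treatment condition.

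**The concern.** The endpoint is meant to describe the effect of a settled dose. If the rules are followed as written, the EOT-A column can mix three kinds of reading: steady state on the final dose, transitional after a recent change, and off drug. A mean change over such a mixture does not estimate the effect of any one dosing condition.

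The responder proportion has a further problem. MYK-224 lowers the gradient by reducing contractility, and the same action is the source of its main safety risk (Table 3.3.1-1, Section 3.3.2). A participant stopped for too much effect on systolic function may still show low gradients at an EOT visit soon afterwards. Nothing in Section 10 prevents that person from being counted as a success. The results are meant to inform dose selection in later studies, so this matters even in a descriptive pilot.

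**Working it through.** **1. How short can the stable phase be?** Inputs: titration cycles of 4 weeks; at least 6 weeks on the target dose, including the 4 weeks of the last cycle; at least 12 weeks in total (Sections 5.1.1.2 and 7.4.1.2); steady state at 21 days (Section 5.1.1.2); a +7-day clinic window (Table 2-3). For k cycles, where the last cycle's dose is the target dose:

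- Total weeks T = max(4k + 2, 12)
- Minimum stable days S = 7 × (T − 4k)

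| k | T (weeks) | S (days) | Stable-phase reductions that leave under 21 days before EOT-A |
|---|---|---|---|
| 1 | max(6, 12) = 12 | 7 × 8 = 56 | those in the last 3 of 8 weeks |
| 2 | max(10, 12) = 12 | 7 × 4 = 28 | those in the last 3 of 4 weeks |
| 3 | max(14, 12) = 14 | 7 × 2 = 14 | all, at minimum length |
| 4 or more | 4k + 2 | 14 | all, at minimum length |

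The exception for k of 3 or more is a reduction on the first stable day with EOT-A slipping by the full window: 14 + 7 = 21 days. Visit windows aside, any treatment period above 12 weeks implies three or more cycles, and Section 5.1 allows about 45 weeks. After a reduction in titration the participant has at least 42 days on the new dose, twice the 21-day mark.

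**2. Permanent discontinuation.** Table 2-4 puts the final dose at EOT-A. Section 8.1.3 puts the EOT visit after the last dose and sets no upper limit on the gap. Both cannot apply to a participant who has stopped. That participant normally has a baseline and a post-baseline value, so stays in the Efficacy/PD set, and is a responder if both gradients are below the cut-offs.

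**3. Post-exercise echo.** The Table 2-4 footnote prefers echo before dosing, and Section 7.1 delays dosing on visit days until assessments are complete. Done in one visit, the reading is pre-dose. If the visit is split, the 72-hour window allows a later day, and the text does not say whether the final dose then waits. Section 9.1.1.3 schedules Part A post-exercise echo only through Tables 2-1 and 2-4, so no other on-treatment reading is scheduled.

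**4. Size, by illustration.** The plan's own figure is 91% power per cohort for a 30 mm Hg post-exercise change (one-sided alpha 0.05, Section 10.2). It cannot be reproduced because N and SD are redacted. With a one-sample t-test many pairs fit the stated powers within 2 points. Three assumed pairs, with two EOT-A readings counted as zero change (an extreme choice) and the SD held fixed:

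| Assumed N, SD | Power at 30 mm Hg | Diluted mean, 30 × (1 − 2/N) | Power after dilution |
|---|---|---|---|
| 15, 37.2 | 91% | 26.0 | 82% |
| 27, 51 | 91% | 27.8 | 87% |
| 42, 64.5 | 91% | 28.6 | 88% |

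Reclassifying one participant as a non-responder moves the proportion by 1/n (90% exact intervals):

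- n = 7 assumed: 4/7 = 57% (23–87%) becomes 3/7 = 43% (13–77%).
- n = 20 assumed: 12/20 = 60% (39–78%) becomes 11/20 = 55% (35–74%).

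**The case against.** The strongest reply has four parts.

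- **The two reduction rules govern different phases.** Section 5.1.1.2 points to Section 7.4.1.2 for the effect of modifications on completion, so the difference may be deliberate, and text just before the key sentence is redacted. This stands against calling it a plain contradiction. It does not remove the consequence for the endpoint.
- **Echo already comes before dosing.** A reader might infer that the post-exercise gradient is routinely read up to 72 hours after the last dose and so is biased toward zero. The Table 2-4 footnote and Section 7.1 do not support that. The problem arises only if the visit is split and the dose is given first.
- **Frequency and direction are unknown.** A reader might infer that the responder rate is inflated. Low gradients soon after stopping would raise it, but gradients that drift back up off drug would lower it. The echocardiographic stopping criteria and N are redacted and no half-life is given. Sections 8.1.1 and 8.1.2 treat stopping as temporary at first and permanent stopping as a last resort.
- **The study is descriptive.** No hypothesis is tested, gradients are listed by participant and summarised by timepoint, and detail is left to a SAP to be finalised before database lock. That makes the gap easy to close, but the text supplied does not close it.

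It would also be too wide to say that every LVOT endpoint rests on EOT-A: the concentration-response endpoint on LVOT gradients runs to EOS-A.

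**Conclusion.** The point holds for the four LVOT-effect measures. Under the stated rules an EOT-A reading can precede the protocol's own 21-day steady state. With three or more titration cycles this applies to almost any reduction made in a stable phase of minimum length. It can also be off drug after permanent discontinuation, for an unlimited interval, and that participant can be counted as a responder. The post-exercise limb is conditional on a split visit, but it matters because no other on-treatment reading is scheduled to replace a compromised one.

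The 14-day result follows from the protocol's figures alone. The power and responder illustrations rest on assumed N, SD and counts and show only the order of effect. How often such readings will occur, and the net direction of bias, cannot be determined from the documents. This should be settled before database lock; it does not undermine the design.

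**What to change.** **Responder proportion.** Count treated participants who permanently stopped before completing Part A treatment, or who have no EOT-A echo, as non-responders. Show the as-observed proportion as a sensitivity analysis.

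**Continuous endpoints.** Keep the observed EOT-A value as the main value. Flag readings taken off drug or less than 21 days after a dose change, and add a sensitivity analysis that excludes them. Do not substitute the last steady-state reading from an earlier dose: that would analyse a participant reduced late at the dose they had left. For the post-exercise gradient there is usually no earlier on-treatment value to use.

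**Visit timing.** At EOT-A, acquire the post-exercise echo on the same day as the resting echo, in the pre-dose order already set out in the Table 2-4 footnote and Section 7.1, and flag any later one.

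**Reconciliation.** Sections 7.4.1.1 and 7.4.1.2 must be reconciled on the time spent on a reduced dose before EOT, and Table 2-4 and Section 8.1.3 on whether EOT-A is on drug. No dose or clinical rule is proposed here.

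**Cost.** SAP wording and one visit-timing instruction, with slightly tighter scheduling at EOT-A and a possibly lower responder rate.
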